## 2.5 Study Center Considerations in the Data Analysis

A study center is defined as a treatment administration site (i.e., LTCF) or group of treatment administration sites under the control and supervision of the same Principal Investigator (PI). There will be no selective pooling of study centers – all sites will be pooled. The study is planned to be conducted at multiple sites.

## 2.6 Documentation and Other Considerations

The data analyses will be conducted using Python and supported statistical packages.

## 3.0 Analysis of Baseline Patient Characteristics

Baseline and demographic characteristics of the safety population will be summarized. Continuous variables (age, baseline height, baseline weight) will be summarized via mean, standard deviation, minimum, median, maximum, and number of non-missing responses. Categorical variables (gender, race, and ethnicity) will be summarized via counts and percentages.

A detailed listing of baseline data for each patient in the safety population will also be provided as shown in Appendix B.

## 4.0 Analysis of Efficacy

### 4.1 Efficacy Variables

The efficacy variables are categorical in nature: the presence or absence of ARI, VRI, or COVID-19 and sequelae during the study period or COVID-19 and sequelae (i.e., hospitalization and death) during the study period.

Symptomatic COVID-19 is defined as an ARI after start of treatment and before the end of the 6-week treatment period associated with detection of SARS-CoV-2 by RT-PCR assay of nasopharyngeal swab.

Symptomatic VRI is defined as an ARI after start of treatment and before the end of the 6-week treatment period associated with detection of any respiratory virus by RT-PCR assay of nasopharyngeal swab.

ARI is defined as  $\geq 0.5$  increase from baseline in mean symptom score in the chest/respiratory domain of the FLU-PRO® instrument; or an increase of at least 0.5 in the mean symptom score of at least two of the following FLU-PRO® domains: body/systemic, nose, throat.

#### Primary Efficacy Variables

There are two primary efficacy variables:

1. The presence or absence of symptomatic COVID-19 disease identified after the start of treatment and before the end of the 6-week treatment period.
2. The presence or absence of symptomatic VRI (including COVID-19) identified after the start of treatment and before the end of the 6-week treatment period.

#### Secondary Efficacy Variables

The secondary efficacy variables are:

1. Hospitalization due to COVID-19 or complications thereof.
2. Mortality due to COVID-19 or complications thereof.
3. The presence or absence of anti-SARS-CoV-2 antibodies at either of the Week 6 or Week 8 visits.

#### Exploratory Efficacy Variables

The exploratory efficacy variables are:

1. Hospitalization due to VRI or complications thereof
2. Mortality due to VRI or complications thereof
3. Presence or absence of an ARI
4. Hospitalization due to ARI or complications thereof

5. Mortality due to ARI or complications thereof.

## 4.2 Efficacy Analysis

### 4.2.1 Primary Efficacy Variables

The study has two primary efficacy endpoints: reduction in symptomatic COVID-19 disease and reduction in all VRI. The study-wise  $\alpha$  level is set at 0.05, allocated with 0.049 to the COVID-19 endpoint and 0.001 to the all VRI endpoint. See Section 2.4 for details on how the study- wise  $\alpha$  level will be allocated to the interim and final analyses. For each endpoint, the following hypotheses will be tested

$$H_0: p_1 = p_2$$

$$H_1: p_1 \neq p_2,$$

here,  $p_1$  represents the probability of symptomatic disease (either COVID-19 or VRI) in the NTZ treatment group and  $p_2$  represents the probability of symptomatic disease in the placebo group.

The proportion of subjects experiencing symptomatic COVID-19 disease in the NTZ treatment group will be compared to the similar proportion in the placebo group using a two-sided CMH test with continuity correction at  $\alpha=0.047$ . The test will be stratified by LTCF. The contingency tables will be provided with rates relative to the treatment margins. A 95% confidence interval for the odds ratio of symptomatic COVID-19 infection in the NTZ group relative to the placebo group will be provided. The risk difference for the treatment groups and a 95% confidence interval for the difference will be provided.

The proportion of subjects experiencing symptomatic VRI infections in the NTZ treatment group will be compared to the similar proportion in the placebo group using a two-sided CMH test, stratified by LTCF with continuity correction at  $\alpha=0.001$ . The contingency tables will be provided with rates relative to the treatment margins. A 95% confidence interval for the odds ratio of symptomatic VRI in the NTZ group relative to the placebo group will be provided. The risk difference for the treatment groups and a 95% confidence interval for the difference will be provided.

CMH analyses of symptomatic COVID-19 disease and symptomatic VRI will be repeated with subjects divided by sex (female or male), age (65- to 79 years or 80 years and over), and race (white or non-white). Estimates and confidence intervals for the odds ratio and relative risk differences will be provided.

Best-case and worst-case sensitivity analyses will be performed as outlined in Section 2.3 above. In addition, a tipping point analysis will be performed, imputing various levels of COVID-19 and VRI infection rates to missing values in the NTZ arm to determine the infection rate at which the study conclusions change.

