8.4.1. Efficacy Analyses

Efficacy analyses will be based on a population consisting of all subjects randomized without a laboratory-detected viral respiratory infection at the baseline visit (intention-to-treat or ITT population).

There will be two primary efficacy analyses:

- The proportion of subjects experiencing COVID-19 in the NTZ treatment group will be compared to that of the placebo treatment group using a two-sided Cochran-Mantel-Haenszel (CMH) chi-square test ($\alpha = 0.049$).
- The proportion of subjects experiencing VRI in the NTZ treatment group will be compared to that of the placebo treatment group using a two-sided CMH chi-square test ($\alpha = 0.001$).

Secondary analyses will be performed as follows:

- Proportions of subjects experiencing hospitalization due to COVID-19 or complications thereof will be compared by treatment group using a two-sided CMH Chi-square test (unadjusted $\alpha = 0.05$).
- Proportions of subjects experiencing mortality due to COVID-19 or complications thereof will be compared by treatment group using a two-sided CMH Chi-square test (unadjusted $\alpha = 0.05$).
- Proportions of subjects (with or without symptoms) testing positive for antibodies to SARS-CoV-2 at either of the Week 6 or Week 8 visits will be compared by treatment group using a two-sided CMH Chi-square test (unadjusted $\alpha = 0.05$).

Exploratory analyses will be performed as follows:

- Proportions of subjects experiencing each of the following will be compared by treatment group using a two-sided CMH Chi-square test (unadjusted $\alpha = 0.05$): (i) hospitalization due to VRI or complications thereof; (ii) mortality due to VRI or complications thereof, (iii) acute respiratory illness (ARI), (vi) hospitalization due to ARI or complications thereof; and (v) mortality due to ARI or complications thereof.

Other analyses may be performed as outlined in the study Statistical Analysis Plan.

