### 1.3 Sample Size

Recent reports of COVID-19 in long-term care facilities in the United States have suggested a high rate of transmission of the SARS-CoV-2 virus, but infection control procedures may significantly decrease transmission (McMichael et al. 2020, Kimball et al. 2020). A recent study of 264 elderly volunteers ( $\geq 65$  years of age) reported 1.6 respiratory tract infections (not laboratory-confirmed) per person-year indicating approximately a 20% probability of respiratory tract infection over a given 6-week period (Mannick et. al, 2018). Infection control procedures in place during the period covered by this clinical trial are also expected to reduce the transmission of other respiratory viruses.

For purposes of calculating sample size, we assume that the proportion of subjects experiencing COVID-19 over a 6-week period is 5%, the proportion of subjects experiencing any VRI is 10%, and that effective prophylaxis will reduce the rate of COVID-19 and other VRIs by 80%.

A Cochran-Mantel-Haenszel (CMH) chi-square test stratifying by 20 LTCFs will have 87.1% statistical power to detect the difference between 5% and 1% rates of occurrence of COVID-19 across all strata at a two-sided alpha of 0.047 with a total sample size of 800, allocated equally to strata (LTCFs) and treatment groups within strata. The statistical

power remains >87% when the number of LTCFs is 5, 10, 16 or 20. The CMH chi-square test has 91% power to detect the difference between 10% and 2% rates of occurrence of VRIs over all strata at a two-sided alpha of 0.001 with 800 subjects allocated equally to 20 LTCFs. Both tests are insensitive to stratum size. Varying the number of subjects per stratum (LTCF) between a minimum of 8 to a maximum of 80 while holding both the effect size and total sample constant results in changes in the third significant figure of the test's power.

A sample size of 800 subjects (400 per treatment group) was selected.

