An interim analysis of effectiveness will be performed when there are at least 25 laboratory-confirmed COVID-19 cases observed among the study participants. If the assumptions made in the power calculations are correct (COVID-19 rate is 0.05 in the placebo group and 0.01 in the NTZ group) we expect to observe only 24 events during the entire study. If this milestone is reached early, it indicates that the assumptions were

conservative and merit review given the high rate of mortality observed from COVID-19 illness in this population. This review will be conducted by the IDMC in accordance with its charter and will encompass both a safety and efficacy determination. In the event that the timing of the interim analysis of effectiveness is near that of the second review for safety and futility, analyses of safety, futility and effectiveness may be performed simultaneously.

O'Brien-Fleming bounds are used to set the Type I error rates for the third interim and final analyses. The interim efficacy review will be performed with  $\alpha = 0.0052$  (overall), allocated 0.005 to the COVID-19 endpoint and 0.0002 to the VRI endpoint. The final data analysis (if the efficacy hypotheses are not rejected at the interim review) will be performed with  $\alpha = 0.048$ , allocated 0.047 to the COVID-19 endpoint and 0.001 to the VRI endpoint. Power at the interim analysis is 31% for the COVID-19 endpoint. If the interim review for efficacy does not occur (i.e., the event count of 25 is not reached or reached too late in the study for the interim review to be useful), the alpha levels for the final analysis will be 0.049 for the COVID-19 endpoint and 0.001 for the VRI endpoint.

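### The fixed 0.049/0.001 alpha split between the two primary endpoints is valid but less efficient than weighted Holm with the same weights; the VRI power gain is about 3 points at the planned effect

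*SAP*

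**What the plan says.** Protocol 8.4.1 states "There will be two primary efficacy analyses": COVID-19 at two-sided 0.049 and VRI at two-sided 0.001, each by a CMH test. SAP 4.2.1 repeats the allocation ("allocated with 0.049 to the COVID-19 endpoint and 0.001 to the all VRI endpoint") and gives the VRI test as a "two-sided CMH test, stratified by LTCF with continuity correction" at 0.001.

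SAP 2.4 sets the levels by look:
- Interim efficacy look (0.0052 in total): "allocated 0.005 to the COVID-19 endpoint and 0.0002 to the VRI endpoint".
- Final analysis after that look (0.048 in total): "allocated 0.047 to the COVID-19 endpoint and 0.001 to the VRI endpoint".
- Final analysis if that look does not take place: "the alpha levels for the final analysis will be 0.049 for the COVID-19 endpoint and 0.001 for the VRI endpoint".

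No section gives a Holm, fallback, hierarchical or graphical rule linking the two primaries, or a reason for holding VRI at 0.001 after COVID-19 has been rejected. SAP 4.1 defines the VRI primary so that it includes COVID-19.

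**The concern.** With a plain weighted Bonferroni split, the alpha assigned to COVID-19 has no further use once COVID-19 is rejected, although it could be passed to VRI without raising the family-wise error. VRI is one of two primary endpoints and appears in the trial's title and objectives.

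The loss grows if the drug works less well than planned. The planned 80% reduction rests on oseltamivir studies in influenza (Protocol 8.1), so a smaller effect is a reasonable case to examine, although the documents do not assume one. The stake is a trial that wins on COVID-19 and misses VRI at 0.001 when a rule with the same family-wise control would have declared both.

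**Working it through.** **Inputs from the documents.** 800 subjects, 400 per arm; COVID-19 5% vs 1%; VRI 10% vs 2%; an 80% reduction in COVID-19 and other VRIs; 20 LTCF strata (SAP 1.3, Protocol 8.1). Alpha sums: 0.049 + 0.001 = 0.05; 0.047 + 0.001 = 0.048; 0.005 + 0.0002 = 0.0052.

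**Step 1: reproduce the plan's power.** Two-proportion normal approximation with pooled null variance and continuity correction 1/400:

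power = Φ[(d − 1/400 − z·se0)/se1], with se0 = √(2·p̄(1−p̄)/400) and se1 = √((p1(1−p1)+p2(1−p2))/400).

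- VRI at 0.001: d = 0.08, se0 = √(2·0.06·0.94/400) = 0.01679, se1 = √((0.09+0.0196)/400) = 0.01655, z = 3.2905. Power = Φ[(0.0775 − 0.05526)/0.01655] = Φ(1.344) = 91.05%. The SAP says "chi-square test has 91% power to detect the difference between 10% and 2% rates of occurrence of VRIs over all strata".
- COVID-19 at 0.047: the same formula gives 87.08%. The SAP says the test "will have 87.1% statistical power to detect the difference between 5% and 1% rates of occurrence of COVID-19".
- Without the correction, VRI at 0.001 gives 93.3% (Protocol 93.9%) and COVID-19 at 0.049 gives 91.3% (Protocol 92.8%).

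The same corrected formula gives VRI power of 99.6% at either 0.048 or 0.05.

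**Step 2: error control.** Weighted Holm is the closed test that rejects the joint null when the COVID-19 p-value is ≤ 0.049 or the VRI p-value is ≤ 0.001 (at most 0.05 by Bonferroni), and each single null at 0.05.

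- Its first step is the plan's own rule, so it rejects whatever the plan rejects.
- Alpha passes only after a rejection, so the chance of at least one rejection is unchanged.
- Under the global null, simulation gave 0.033 for both rules with the continuity correction, and 0.048 for both without it.

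**Step 3: VRI power.** Simulated two-sided corrected CMH, 20 strata of 40, levels 0.049/0.001, no interim look. Placebo risk is 5% COVID-19 plus 5% other VRI (10% − 5%). There were 200,000 trials per row, except 40,000 for the 70% and 80%/50% rows.

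| True reduction | Fixed split | Weighted Holm | Gain (points) |
|---|---|---|---|
| 80% on both (planned) | 94.0% | 96.8% | 2.8 |
| 70% on both (assumed) | 74.7% | 85.0% | 10.3 |
| 60% on both (assumed) | 46.0% | 63.6% | 17.7 |
| 50% on both (assumed) | 22.1% | 41.0% | 18.8 |
| 80% COVID-19, 50% other (assumed) | 60.8% | 89.4% | 28.6 |
| 80% COVID-19, 0% other (assumed) | 8.4% | 48.8% | 40.4 |

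Gains are taken before rounding. The simulated CMH power is about 3 points above the formula in Step 1; both columns come from the same trials, so the comparison is not affected. At 0.047/0.001 the planned row is almost the same (93.9% to 96.7%). Passing alpha the other way, from VRI to COVID-19, adds little: COVID-19 power goes from 90.4% to 90.6% at the planned effect.

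**Step 4: how often the rule matters.** Trials that win COVID-19 and miss VRI under the fixed split: at the planned effect 90.4% − 87.6% = 2.8%; at 60% on both, 56.2% − 37.7% = 18.5%.

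**The case against.** **The plan is not in error.** The split is pre-specified, valid, applied to VRI consistently at the final analysis, and meets its stated power. This stands in full. A reader might infer that the trial will often win COVID-19 and fail VRI because of unused alpha. The documents do not support that: they assume one common 80% reduction, at which it happens in 2.8% of trials. The larger figures need effects that the documents do not state.

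**The endpoints are nested.** This is the strongest objection. A reader might infer that the 0.001 level costs power and buys nothing. That is true of the family-wise rate only. VRI includes COVID-19, so after a COVID-19 win a VRI test at 0.05 is nearly automatic: it succeeds in over 99.9% of such trials at the planned effect and 98.5% at 60%. If the drug worked on COVID-19 alone, VRI would be declared in 54% of COVID-19-winning trials instead of 9%. At 80%/50%, only 4% of the extra VRI wins show a non-COVID difference at p < 0.05, against 58% of the wins under the fixed split.

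These are not false rejections. With 80% efficacy on COVID-19 and none elsewhere, the all-VRI rates are 10% and 1% + 5% = 6%, so the SAP's stated VRI null is untrue. What stands is a limit on interpretation: the 0.001 level does in practice demand more evidence beyond the COVID-19 component, and passing alpha removes that demand.

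**The interval.** A reader might also count it against the split that the planned 95% interval for VRI could exclude no effect while the 0.001 test fails. That follows from showing 95% intervals beside any smaller alpha. It is a separate matter, and alpha passing would not remove it when COVID-19 is not rejected.

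**Conclusion.** The fixed split is valid but inefficient. Weighted Holm with the same weights dominates it for rejecting the two stated hypotheses, at the same family-wise 0.05. The gain in VRI power is about 3 points at the planned effect, about 10 at a 70% reduction and about 18 at 60%.

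The dominance does not depend on any effect size; the size of the gain does. The simulated figures assume 800 analysed subjects, equal strata, equal COVID-19 and other-VRI risk on placebo, and no interim look. Dropout and the exclusion of subjects with a respiratory virus at baseline would lower power under both rules. The SAP's interim and final levels are taken as given.

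The change is worth making only together with the non-COVID VRI results. Without them, a VRI win obtained by alpha passing should not be read as broad-spectrum efficacy.

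**What to change.** Before any unblinding, write one rule into SAP 4.2.1, SAP 2.4 and Protocol 8.4.1. If COVID-19 is rejected at its own level, test VRI at the full level for that analysis; if VRI is rejected first, do the same for COVID-19.

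| Analysis | COVID-19 start | VRI start | Full level after the other is rejected |
|---|---|---|---|
| Interim efficacy look | 0.005 | 0.0002 | 0.0052 |
| Final, after that look | 0.047 | 0.001 | 0.048 |
| Final, no interim efficacy look | 0.049 | 0.001 | 0.05 |

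SAP 2.4 should also say how VRI is concluded if the trial ends at the interim look. The same edit should make the COVID-19 level in SAP 4.2.1, which is fixed at 0.047, follow SAP 2.4, which uses 0.049 when no interim efficacy look occurs.

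Pre-specify, beside the VRI test, the non-COVID VRI rates by arm and the treatment difference with a confidence interval, stating how subjects with both SARS-CoV-2 and another virus are counted. State that a VRI win reached by alpha passing is not a broad-spectrum claim without these results.

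No extra subjects or data are needed. It does change the decision rule for a primary endpoint, so it needs a protocol amendment as well as a SAP revision. If the sponsor prefers to keep VRI at 0.001 so that a VRI win carries more evidence beyond COVID-19, the SAP should give that reason.

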8. STATISTICAL CONSIDERATIONS

8.1. Sample Size Calculations

Recent reports of COVID-19 in long-term care facilities in the United States have suggested a high rate of transmission of the SARS-CoV-2 virus, but infection control procedures may significantly decrease transmission (McMichael et al. 2020, Kimball et al. 2020). A recent study of 264 elderly volunteers (≥ 65 years of age) reported 1.6 respiratory tract infections (not laboratory-confirmed) per person-year indicating approximately a 20% probability of respiratory tract infection over a given 6-week period (Mannick et. al, 2018). Infection control procedures in place during the period covered by this clinical trial are also expected to reduce the transmission of other respiratory viruses.

For purposes of calculating our sample size, we assume that the proportion of subjects experiencing COVID-19 over a 6-week period is 5%, the proportion of subjects experiencing any VRI is 10%, and that effective prophylaxis will reduce the rate of COVID-19 and other VRIs by 80%. Influenza prophylaxis studies of oseltamivir have resulted in approximately 80% reduction of influenza illness among residents of long-term care facilities (see Tamiflu® prescribing information).

A Cochran-Mantel-Haenszel (CMH) chi-square test stratifying by 20 LTCFs will have 92.8% statistical power to detect the difference between 5% and 1% rates of occurrence of COVID-19 over all strata at an alpha of 0.049 with a total sample size of 800, allocated equally to strata (LTCFs) and treatment groups within strata. The statistical power remains >92% when the number of LTCFs is 5, 10, 16 or 20. The CMH chi-square test has 93.9% power to detect the difference between 10% and 2% rates of occurrence of VRIs over all strata at an alpha of 0.001 with 800 subjects allocated equally to 20 LTCFs. Adjusting the stratum size to assume unequal allocation while holding the effect size and total sample size constant results in negligible changes (i.e., changes in the third significant figure) in the study power.

A sample size of 800 subjects (400 per treatment group) was selected.

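### SAP 4.2.1 puts a continuity correction on both primary CMH tests that Protocol 8.4.1 does not mention, at a cost in alpha and power; separately, the Protocol 8.1 power figures appear to be one-sided

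*SAP*

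**What the plan says.** **Test.** Protocol 8.4.1 compares both primary proportions "using a two-sided Cochran-Mantel-Haenszel (CMH) chi-square test", at 0.049 for COVID-19 and 0.001 for VRI. It does not mention a continuity correction. SAP 4.2.1 specifies for COVID-19 a "two-sided CMH test with continuity correction", stratified by LTCF, at 0.047, and gives the VRI test the same correction at 0.001. Neither document gives a reason for it, and the SAP revision history does not list it.

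**Power.** Protocol 8.1 states "92.8% statistical power to detect the difference between 5% and 1% rates of occurrence of COVID-19 over all strata at an alpha of 0.049" and "93.9% power to detect the difference between 10% and 2% rates of occurrence of VRIs over all strata at an alpha of 0.001". It gives neither the sidedness of these alphas nor whether a correction is included. For the same 800 subjects, rates and 20 facilities, SAP 1.3 says the COVID-19 test "will have 87.1% statistical power to detect the difference between 5% and 1% rates of occurrence of COVID-19" at a two-sided 0.047, and gives 91% for VRI at a two-sided 0.001.

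**Alpha.** Under SAP 2.4 the final COVID-19 test uses 0.047 if the interim efficacy review takes place and 0.049 if it does not. VRI uses 0.001 in both cases.

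**The concern.** There are two separate problems.

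1. The corrected and uncorrected CMH tests are different rejection rules. With few events the half-unit correction is large relative to the standard deviation of the test statistic, so the actual type I error falls well below the nominal level and power falls with it. SAP 2.4 expects only 24 COVID-19 events in the whole study, so one or two cases can decide the primary result. It also divides alpha to the fourth decimal, which means little if the test then leaves a large part of it unused.

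2. The two documents promise different power for the same endpoint, sample size and rates. A reader of the protocol alone would expect nearly 93% for COVID-19, while the SAP says 87.1%. It matters which figure belongs to the planned test, and why they differ.

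**Working it through.** **Inputs.** n = 400 per arm and 20 facilities (Protocol 8.1, SAP 1.3). COVID-19 rates are 5% and 1%; VRI rates are 10% and 2%. Alphas are 0.049, 0.047 and 0.001. The documents give no null rates, so common rates of 1% to 10% are assumed.

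**Step 1: reproduce the stated powers.** With equal strata, the normal approximation for the CMH test is

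power = Φ((d − c − z·se0)/se1)

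where d is the rate difference, se0 the pooled and se1 the unpooled standard error, and c = 1/n = 0.0025 with the correction or 0 without. The number of strata drops out, which fits both documents' statements that it hardly matters.

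- COVID-19: d = 0.04, se0 = √(2·0.03·0.97/400) = 0.01206, se1 = √((0.05·0.95 + 0.01·0.99)/400) = 0.01198.
- VRI: d = 0.08, se0 = √(2·0.06·0.94/400) = 0.01679, se1 = √((0.1·0.9 + 0.02·0.98)/400) = 0.01655.

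Two examples for COVID-19:

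- One-sided 0.049, corrected: (0.04 − 0.0025 − 1.6546·0.01206)/0.01198 = 1.464, so power is 92.84%.
- Two-sided 0.047, corrected: (0.04 − 0.0025 − 1.9863·0.01206)/0.01198 = 1.130, so power is 87.08%.

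| Endpoint, alpha | One-sided, uncorrected | One-sided, corrected | Two-sided, uncorrected | Two-sided, corrected | Stated |
|---|---|---|---|---|---|
| COVID-19, 0.049 | 95.28% | **92.84%** | 91.26% | 87.46% | 92.8% (protocol) |
| COVID-19, 0.047 | 95.08% | 92.57% | 90.97% | **87.08%** | 87.1% (SAP) |
| VRI, 0.001 | 95.52% | **93.91%** | 93.25% | **91.05%** | 93.9% (protocol), 91% (SAP) |

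Both protocol figures match the one-sided corrected column, and both SAP figures the two-sided corrected column.

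**Step 2: split the gap.** On the best-fitting reading, moving from one-sided to two-sided at 0.049 takes 92.84% to 87.46% (5.4 points). Moving from 0.049 to 0.047 takes it to 87.08% (0.4 points). The correction is present at both ends and contributes nothing.

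**Step 3: what the correction does at a fixed two-sided alpha.** By formula it costs 90.97 − 87.08 = 3.9 points for COVID-19 at 0.047 and 93.25 − 91.05 = 2.2 points for VRI. Simulating the stratified test itself, with 20 strata of 40, gives:

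| | Uncorrected | Corrected |
|---|---|---|
| COVID-19 size at nominal 0.047, null rates 1% to 10% | 0.043 to 0.048 | 0.017 to 0.035 |
| VRI size at nominal 0.001, null rates 2% to 10% | 0.0005 to 0.0009 | 0.0001 to 0.0006 |
| COVID-19 power at 0.047 | 94.0% | 90.2% |
| VRI power at 0.001 | 95.6% | 93.9% |

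Corrected COVID-19 size rises with the null rate: about 0.018 at 1%, 0.023 at 2%, 0.030 at 5% and 0.035 at 10%. Simulated power lies 2 to 3 points above the formula, but the cost of the correction is about the same.

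**Step 4: in cases.** The planning rates imply 400·0.01 = 4 NTZ and 400·0.05 = 20 placebo cases. Take 4 NTZ cases and ignore strata, so that the variance for m cases in total is m(800 − m)/(4·799).

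- 12 placebo cases, uncorrected: (8 − 4)²/3.925 = 4.08, p = 0.044. This rejects at 0.047.
- 13 placebo cases, corrected: (8.5 − 4 − 0.5)²/4.165 = 3.84, p = 0.050. This does not reject at 0.047 or 0.049.
- 14 placebo cases, corrected: (9 − 4 − 0.5)²/4.404 = 4.60, p = 0.032. This rejects.

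The corrected test needs two more placebo cases.

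**The case against.** **A stronger reading to avoid.** A reader might infer that the protocol's power is that of the uncorrected test, and that the fall from 92.8% to 87.1% is the price of the correction. The figures do not support this. Uncorrected two-sided power by the same formula is 91.26% and 93.25%, and neither is the protocol's number, whereas the one-sided corrected formula gives both to the digit. The uncorrected reading cannot be strictly excluded, because Protocol 8.1 states neither sidedness nor correction and 91.3% is within two points of 92.8%. It is still the poorer fit, and the gap should not be attributed to the correction.

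**The case for leaving the plan alone.** Protocol 8.4 describes the methods only briefly and defers detail to the SAP, and the name CMH chi-square does not exclude a correction. The corrected test is a standard, pre-specified choice that errs only towards caution, which is defensible with about one expected event per facility. SAP 1.3 already states power for the corrected two-sided test, so the SAP agrees with itself and hides nothing. At 87% to 90% for COVID-19 and 91% to 94% for VRI, the trial is not underpowered on its own assumptions.

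**What stands of it.** All of that is fair, and it limits the point to efficiency and consistency. The correction does give some protection: the uncorrected test is not strictly conservative. But simulated size exceeds nominal by only about 0.001, reaching 0.048 at 0.047 and 0.050 at 0.049, which is little return for nearly 4 points of power. Deferring detail to the SAP also does not explain a protocol power figure that appears to be one-sided beside a two-sided test.

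One caution: simulated two-sided corrected VRI power is 93.9%, the same number as the protocol's. Simulation does not explain the protocol's pair, however. At two-sided 0.049 it gives COVID-19 power of 90.3% with the correction and 94.2% without, not 92.8%.

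**Conclusion.** The point holds in two separate parts.

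1. The SAP's correction, which the protocol does not mention, makes both primary tests clearly stricter than their nominal levels. Actual COVID-19 size is roughly 0.017 to 0.035 at 0.047. Power falls by about 4 points for COVID-19 and about 2 for VRI.

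2. The pair of powers in Protocol 8.1 does not describe the two-sided test to be run. It is best explained by a one-sided alpha with correction. The two-sided corrected values by the same formula are 87.5% at 0.049, 87.1% at 0.047 and 91.05% for VRI.

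The size figures rest on assumed common null rates and 20 equal strata of 40. The power figures rest on the plan's own rates. That the protocol's alpha was used one-sided is inferred from the numerical match; the protocol does not say so. Because the error is conservative, the change is advisable and not a condition of a valid trial.

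**What to change.** **Preferred.** Delete the continuity correction from both primary tests in SAP 4.2.1. Restate power in Protocol 8.1 and SAP 1.3 for the two-sided uncorrected test: by formula about 91.0% at 0.047, 91.3% at 0.049 and 93.3% for VRI at 0.001. State sidedness, absence of a correction and method of calculation beside each figure, since simulation gives values 2 to 3 points higher. The cost is a wording change before unblinding, and a size that is no longer strictly conservative (at most about 0.048 at 0.047 and 0.050 at 0.049 in simulation).

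**If the correction is kept.** Name it in Protocol 8.4.1 and restate Protocol 8.1 as two-sided: 87.5% at 0.049 (87.1% at 0.047) for COVID-19 and 91% for VRI. The protocol's claim that "The statistical power remains >92% when the number of LTCFs is 5, 10, 16 or 20" must then change as well. This too is only wording, but the loss of alpha and power remains.

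Either way, the two documents should describe one primary test and give one power figure per endpoint and alpha.
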